5. DATA AND ANALYSIS CONSIDERATIONS

5.1. General Principles

All demography and safety data will be presented by the safety population, except for the DLT reporting which will be based on the DLT evaluable population. Assessment of anti-tumor activity will be based on the Efficacy Population and PK data will be presented by the PK Population.

Most of the analyses will be descriptive in nature. Unless stated otherwise, continuous variables will be summarized using descriptive statistics (number of patients, mean, standard deviation, median, lower and upper quartile, minimum and maximum values) and the number and percentage of patients will be used for categorical variables. In general, missing data will be considered as missing and will not be imputed. Unless stated otherwise, percentages will be calculated out of the number of patients in the relevant analysis population.

Baseline will be the last assessment of the variable under consideration prior to first dose of RP-6306.

Unless stated otherwise, safety and efficacy data will be presented by assigned dose/schedule.

After determination of RP2D dose(s), safety and efficacy data may also be summarized by grouping dose levels based on RP2D and clinical relevance.

All DLT rates will be summarized by the assigned initial dose levels.

Summary statistics will be presented to the following degree of precision unless otherwise specified:

	Degree of Precision
Mean, Geometric mean, Median, Quartiles, Confidence limit boundaries	One more decimal digit than the raw data.
Standard deviation, Standard error	Up to 2 more than the raw data
Minimum, Maximum	The same decimal digit as the raw data.
Percentage	One decimal place. A percentage of 100% will be reported as 100%. Percentages of zero will be reported as 0.

5.2. Study Day and Analysis Visit

Study Day will be calculated from the reference start date (defined as the date of first dose of study drug), and will be used to show start/stop day of assessments/events:

Study Day = (date of assessments/events - reference start date) if event/assessment is prior to the reference start;

Study Day = (date of assessments/events - reference start date + 1) if event/assessment is on or after the reference start.

There is no Study Day 0.

5.2.1. Analysis Visit

Baseline value will be the latest non-missing result obtained on or before the first dose of study treatment. The nominal visits will be used as analysis visits for the purpose of summarizing data over scheduled visit. If visits are clearly defined, no windowing algorithm will be used.

All recorded data will be included in the listings.

5.3. Handling of Missing Data

There will be no imputation of incomplete or missing data other than the dates mentioned below. No imputation will be performed for missing data elements for by-patient listings. However, the imputation will be implemented for summary tabulations, when applicable.

5.3.1. Missing/Partial Dates in Adverse Events

Missing Data Imputation for Adverse Event Start Dates

If the stop date is non-missing and the imputed start date is after the stop date, the stop date will be used as the start date.

- (1) Missing day only
- If the month and year are the same as the month and year of the first dose date, the first dose date will be used.
- If the month and year are before the month and year of the first dose date, the last day of the month will be assigned to the missing day.
- If the month and year are after the month and year of the first dose date, the first day of the month will be assigned to the missing day.
- (2) Missing day and month
- If the year is the same as the year of the first dose date, the first dose date will be used.
- If the year is prior to the year of the first dose date, December 31 will be assigned to the missing fields.
- If the year is after the year of the first dose date, January 1st will be assigned to the missing fields.
- (3) Missing day, month, and year (or only year)
- The first dose date will be used.

Missing Data Imputation for Missing Adverse Event Stop Date

If the start date is non-missing and the imputed stop date is before the start date, the start date will be used. If the death date is available and the imputed stop date is after the death date, the death date will be used.

- (1) Missing day only
 - The last day of the month will be assigned as the missing day.
- (2) Missing day and month
 - December 31 will be assigned to the missing fields.
- (3) Missing day, month, and year (or only year)

• The event will be regarded as ongoing.

5.3.2. Missing/Partial Dates in Concomitant Medication

Missing Data Imputation for Concomitant Medication Start Dates

If the stop date is non-missing and the imputed start date is after the stop date, the stop date will be used as the start date.

(1). Missing day only

- If the month and year are the same as the month and year of the first dose date, the first dose date will be used.
- If the month and year are before the month and year of the first dose date, the last day of the month will be assigned to the missing day.
- If the month and year are after the month and year of the first dose date, the first day of the month will be assigned to the missing day.

(2). Missing day and month

- If the year is the same as the year of the first dose date, the first dose date will be used.
- If the year is prior to the year of the first dose date, December 31 will be assigned to the missing fields.
- If the year is after the year of the first dose date, January 1st will be assigned to the missing fields.
- (3). Missing day, month, and year (or only year)
 - Do not impute.

Missing Data Imputation for Missing Concomitant Medication Stop Date

If the start date is non-missing and the imputed stop date is before the start date, the start date will be used. If the death date is available and the imputed stop date is after the death date, the death date will be used.

- (4) Missing day only
 - The last day of the month will be assigned as the missing day.
- (5) Missing day and month
 - December 31 will be assigned to the missing fields.
- (6) Missing day, month, and year
 - Do not impute.

5.3.3. Missing/Partial Dates during Screening Visit or Prior to Study Treatment

The following rules apply to dates recorded during the screening visits (e.g., prior therapies/medications, initial diagnosis):

- (1) Missing day only
 - The first day of the month will be used if the year and the month are the same as those for the first dose of study drug. Otherwise, the 15th will be used.
- (2) Missing day and month
 - If the year is the same as the year of the first dose of study drug, the 15th of January will be used unless it is later than the first dose, in which case the date of the first of January will be used.
 - If the year is not the same as the year of the first dose of study drug, the date of the first of July will be used, unless other data indicates that the date is earlier.
- (3) Missing day, month, and year
 - No imputation will be applied.

If the imputed date is later than the first dose, then the date of the first dose will be used.

5.3.4. Missing/Partial Dates in Post-study Anticancer Therapy

Post-study therapy/radiotherapy start date:

If the stop date is non-missing and the imputed start date is after the stop date, the stop date will be used as the start date.

- If year is missing (or completely missing), do not impute.
- If year is present and month and day are missing:
 - If year is the same as the year of last dose date, impute as the last dose date + 1.
 - If year is greater than the year of last dose date, impute as January 1st.
- If year and day are present and month is missing:
 - If year is the same as the year of last dose date, and day is not greater than the day of last dose date, impute the month as the month of last dose date + 1.
 - If year or day is greater than the year or day of last dose date, impute the month as the month of last dose date.
- If year and month are present and day is missing:
 - If year and month are the same as the year and month of last dose date, impute as last dose date + 1.
 - If year or month is greater than the year or month of last dose date, impute day as first day
 of the month.

Post-study therapy/radiotherapy end date:

If the start date is non-missing and the imputed stop date is before the start date, the start date will be used. If the death date is available and the imputed stop date is after the death date, the death date will be used.

- If year is missing (or completely missing), do not impute.
- If (year is present and month and day are missing) or (year and day are present andmonth is missing, impute as December 31st.
- If year and month are present and day is missing, impute day as last day of the month.
- If the imputed end date is earlier than the observed/imputed post-study therapy/radiotherapy start date, the end date will be imputed as the same as the start date.

5.3.5. Missing/Partial Last Dose Date

Missing/incomplete last dose date from the treatment discontinuation page will be imputed as follows:

- 1. *Missing day only*
 - If the treatment discontinuation reason is death, the death date will be used.

Else if the last available dosing date from dosing data matches the partial last dose date from the treatment discontinuation page, the last available dosing date will be used.

- Else the first day of the month will be used.
- (2) Missing day and month
 - If the treatment discontinuation reason is death, the death date will be used.
 - Else if the last available dosing date from dosing data matches the partial last dose date from the treatment discontinuation page, the last available dosing date will be used.
 - Else January 1st will be used.
- (3) Missing day, month and year
 - If the treatment discontinuation reason is death, the death date will be used.
 - Else the last available dosing date will be used.

The imputed last dose date will be compared to the available study discontinuation date and the data cut off date. Then the earliest date will be used.

5.3.6. Relationship and Severity Imputation Rules for Adverse Events

Imputation will not be made for data listings and datasets. Missing severity and relationship will not be imputed. All AEs are expected to have non-missing severity (to toxicity grade) and relationship at the time of database lock.

6. DISPOSITION, DEVIATIONS AND PATIENT CHARACTERISTIC DATA

An overall patient disposition summary will be presented for all subjects to show the number of unique patients who entered the study.

In addition, patient disposition will be presented by Module 1a or 1b and by dose/schedule with percentages based on the safety population. The following information will be presented for disposition:

- Included in each analysis population (DLT evaluation, safety, Efficacy and PK)
- Ongoing/discontinued study treatment at the data cut off
 - Including reasons for discontinuation of treatment as per the eCRF
- Ongoing/withdrawn/completion from study at the data cut off
 - Including reasons for study termination as per the eCRF

Disposition data will be listed for all patients and will include patient status, date of discontinuation from treatment, date of withdrawal from study and reason for treatment discontinuation and study withdrawal. In addition, the number and percentage of subjects by country and site will be summarized.

6.1. Protocol Deviations

There is no per protocol analysis population defined for this study, therefore patients will not be excluded from the data analysis and reporting based on deviations.

Any important deviations discovered during the trial either through the data collected on eCRFs or monitoring visits/reports will be listed and summarized. Deviation data may be exported into the database via third party data such as an excel file used by study monitors to track deviations (e.g., deviations collected via the clinical study management system, CTMS).

The following deviations will be considered important deviations:

- Patients who entered the study but did not fulfil the entry criteria.
- Treatment deviations such as wrong treatment received or incorrect dose during the study. Note, treatment delays or changes due to AE management are not considered treatment deviations. A review of relevant data may be required to confirm all important deviations in this category.
- Patients who received a prohibited concomitant treatment, including prohibited anti-cancer treatments.

If a patient has a delay in treatment or misses cycles due to the impact of COVID-19, their eligibility for inclusion in the analysis will be decided on a case-by-case basis prior to database lock.

Following review of all reported deviations and associated data and prior to database lock, other important deviation categories may be added. Only important deviations will be listed and summarized if appropriate. If the number of important deviations are few (<=5 patients), only listing will be provided.

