All safety assessments must be carried out at the clinical trial site prior to the first treatment cycle and study drug being dispensed to the patient for the first time		reviewed by an Investigator to verify if the patient is fit for treatment continuation. Communication pathway should be agreed to with local office, including when to expect results, prior to completion of the assessment. • Imaging assessment and protocolmandated tumor samples or malignant fluid collection should be conducted as soon as they are considered safe and feasible; out of window assessments are preferable to a missed assessment. Visit changes will be considered a Protocol Deviation related to the unforeseen circumstances, such as COVID-19, and should be documented by study standard procedures. Performing an out of window imaging assessment is preferable to missing the assessment entirely.
AE Reporting	Collecting and Recording Adverse Events	If physical visits are reduced or postponed, the Investigators will continue collecting AEs from the patient through alternative means, e.g., by phone calls or telemedicine visits, as appropriate.
Protocol Deviations	Protocol Deviations	Protocol deviations (e.g., out of visit windows, etc.) should be captured per the usual study/institutional requirements.

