3. INVESTIGATIONAL PLAN

3.1. Overall Study Design and Plan

This is a multicenter, open-label, Phase 1 study to evaluate the safety and preliminary efficacy of RP-6306, a first-in-class, membrane-associated tyrosine- and threonine-specific Cdc2-inhibitory kinase (PKMYT1) inhibitor, given on a continuous or, if necessary, intermittent schedule in combination with FOLFIRI for the treatment of patients with locally advanced or metastatic solid tumors (Figure 1). Eligible patients must have a CRC, GI, esophageal tumor, or other solid tumors harboring CCNE1 amplification, deleterious mutation in FBXW7 and/or other genetic alterations with mechanistic rationale agreed upon by the Sponsor and the Investigator and, in the opinion of the Investigator, are candidates for FOLFIRI treatment.

The study will follow a Bayesian Optimal Interval (BOIN) drug combination design to identify the MTD (dose level and dosing schedule for Module 1a and, if necessary, Module 1b) of RP-6306 and FOLFIRI. Backfill cohorts with specific molecular alterations or cancer types will be enrolled to further evaluate the PK, pharmacodynamic and mechanism of action biomarkers, safety and tolerability, and preliminary efficacy of the combination, as agreed upon by the Investigators and Safety Review Committee (SRC). The totality of safety, PK, pharmacodynamic, and preliminary efficacy data from each module will be used to establish a preferred RP2D and schedule.

Figure 1: Module 1 Study Schema

[figure not shown]
CCNE1=Cyclin E1; CRC=colorectal; FBXW7=F-box and WD repeat domain containing 7; GI=gastrointestinal; QD=once daily; RP2D=recommended Phase 2 dose.

Note: Additional schedules may be tested based on safety, tolerability, and drug exposure data generated in Modules 1a and 1b.

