8.2. Efficacy Analysis Methods

For overall response rate, ORR, and CBR, the number and percentage of patients along with an exact binomial 95% confidence interval (CI), using the Clopper-Pearson method, will be presented.

In general, summary of all efficacy endpoints will be provided by dose level separately for Module 1a and 1b patients.

The assessment of tumor efficacy will be based on the measurements recorded by the investigator.

A summary of the best objective response will be presented which will include the number and percentage of patients with a best response of CR, PR, SD, PD and NE.

Time-to-event endpoints (PFS) will be analyzed using the KM method and results will be summarized by the 25th, 50th and 75th percentiles, if estimable, with associated 2-sided 95% CIs. KM plots will be provided. For PFS, the number (%) of patients with an event and the number (%) of patients censored will also be presented. The rate of PFS at 16 weeks and 24 weeks will be derived from the corresponding Kaplan-Meier curves. The KM analyses for DOR may be replaced by descriptive summary of median, and quartiles with individual listing for responders if total confirmed responders are few and less than 5 patients.

Maximum reduction in tumor size will be summarized by n, mean, standard deviation, median, 25th quartile and 75th quartile, minimum and maximum. The spider plots displaying change in tumor size over time for each patient will also be provided for each module and dose/schedule group as described above.

In addition, waterfall plots showing the best percentage change from baseline (largest decrease or smallest increase in the absence of a decrease) in the sum of the TL sizes will be produced for each module by dose/schedule group indicating each patient' best objective response.

Swimmer plots will be produced for each module and dose/schedule group to show the duration of study treatment per patient with indicators for timing of response, progression or death, where applicable.

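### SAP 6.1 rules out exclusions for deviations, then lets COVID-affected patients be kept or dropped case by case, with no criteria, against its own fixed population definitions

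*SAP*

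**What the plan says.** SAP 6.1 opens by noting that no per-protocol population is defined and concludes: "therefore patients will not be excluded from the data analysis and reporting based on deviations". It then lists the deviations that count as important and makes one exemption among delays: "treatment delays or changes due to AE management are not considered treatment deviations".

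Further down the same section comes a separate rule. The trigger is: "If a patient has a delay in treatment or misses cycles due to the impact of COVID-19". The consequence is: "their eligibility for inclusion in the analysis will be decided on a case-by-case basis prior to database lock". Nothing more is said about who decides, on what grounds, for which population, or whether results will also be shown with everyone included.

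The analysis populations are set by fixed rules:

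- **DLT Evaluable (SAP 4.1):** patients with a DLT in the first two cycles, plus those who received at least 75% of planned RP-6306 and 100% of planned FOLFIRI, completed the safety evaluations and were observed to Day 28.
- **Efficacy (SAP 4.2):** treated patients with local confirmation of the genomic alteration and either a post-baseline tumor assessment or treatment discontinuation for clinical progression or death before one.
- **Safety (SAP 4.3):** everyone who took at least one dose.

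Protocol Appendix 7 adds, in its row on study assessments: "Visit changes will be considered a Protocol Deviation related to the unforeseen circumstances, such as COVID-19".

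**The concern.** A plan that promises no exclusion for deviations cannot also leave one class of patients to be kept or dropped by judgement. The choice comes late, and nothing shields those who make it from the results. SAP 3.1 describes the design thus: "This is a multicenter, open-label, Phase 1 study to evaluate the safety and preliminary efficacy of RP-6306". SAP 8.2 adds: "The assessment of tumor efficacy will be based on the measurements recorded by the investigator". Toxicities and responses are therefore known as they occur, and a deadline of database lock gives no protection.

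What is at stake is the set of efficacy and safety summaries by module and dose level. These groups are small enough for one patient to be visible in a percentage, and those summaries feed the choice of RP2D. SAP 1 gives credibility through pre-specification as the plan's purpose; an inclusion rule without criteria works against it.

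**Working it through.** The plan states no figure on this point, so there is none to reproduce. The check is a comparison of texts, followed by an illustration of size.

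**Step 1. Does anything reconcile the two statements in SAP 6.1?** The general rule covers deviations without qualification. The COVID sentence sits under the Protocol Deviations heading, and the only delays exempted from being treatment deviations are those due to AE management. Protocol Appendix 7 gives partial support: it classes COVID-related visit changes as deviations, but a visit change is not the same as a delayed or missed treatment cycle. The contradiction therefore rests on SAP 6.1 itself. No other section limits or explains the COVID sentence.

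**Step 2. Do the population definitions allow the discretion?** SAP 4.1, 4.2 and 4.3 contain no COVID exception, and neither do the definitions in the protocol synopsis. A treated patient belongs to the Safety Population by rule. A treated patient who meets the SAP 4.2 conditions belongs to the Efficacy Population by rule. Dropping either would breach Section 4.

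**Step 3. Is the discretion needed?** Existing rules already deal with the consequences of a COVID interruption:

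- SAP 4.1 settles DLT evaluability when doses are missed in the first two cycles.
- SAP 8.1.8 and Table 5 set the PFS event or censoring date when a death follows a long gap in tumor assessments.
- Dose intensity in SAP 7.2 is designed to capture shortfalls in RP-6306 dosing.

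**Step 4. How large could the effect be?** With r responders among n patients, ORR = r/n.

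- Dropping one non-responder gives r/(n−1), a rise of r/[n(n−1)].
- Dropping one responder gives (r−1)/(n−1), a fall of (n−r)/[n(n−1)].

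The first example takes n = 6, the minimum that SAP 8 expects at the RP2D from dose finding, and assumes r = 1. The second takes n = 14, which is those 6 plus one backfill cohort at the protocol's ceiling of 8, and assumes r = 3. Intervals are Clopper-Pearson, as in SAP 8.2.

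| Case | Responders/n | ORR | Exact 95% CI |
|---|---|---|---|
| n = 6, all kept | 1/6 | 16.7% | 0.4 to 64.1% |
| one non-responder dropped | 1/5 | 20.0% | 0.5 to 71.6% |
| the responder dropped | 0/5 | 0% | 0 to 52.2% |
| n = 14, all kept | 3/14 | 21.4% | 4.7 to 50.8% |
| two non-responders dropped | 3/12 | 25.0% | 5.5 to 57.2% |
| one responder dropped | 2/13 | 15.4% | 1.9 to 45.4% |

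For n = 6 the shifts are 1/30 = 3.3 points up and 5/30 = 16.7 points down. For 0/5 the upper limit is 1 − 0.025^(1/5) = 52.2%. The same arithmetic applies to the incidence of an adverse event at a dose level.

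**The case against.** Four points can be made for the plan.

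**The sentence may be a specific exception, or only a promise to check affected patients against Section 4.** Either reading is possible. If it is an exception, it still lacks criteria. If it is a check, the rules in Section 4 leave nothing to decide case by case, and the text should say so. Both readings lead to the same repair.

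**Nothing says that outcomes will be consulted.** This stands. The documents support only that the exclusion is potentially outcome-aware, because no safeguard prevents it.

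**The effect is small and would not be hidden.** This largely stands. The intervals above overlap almost entirely, ORR is a secondary endpoint, and most analyses are descriptive (SAP 5.1). SAP 6 reports the number of patients in each population, and SAP 5.2.1 puts all recorded data in the listings. However, neither requires the reason for an exclusion or the result with everyone included.

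**Dose finding is protected.** A reader might infer that the sentence could move a BOIN decision. In SAP Table 2, 1 DLT in 6 means escalate, 2 in 6 means de-escalate, and 1 in 5 means stay, so removing one patient appears to change the action. The documents do not support this:

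- Table 2 is applied during the trial with SRC guidance. A decision before lock about inclusion in the analysis cannot undo a cohort decision already acted on.
- SAP 4.1 keeps every patient with a DLT in the first two cycles, so 2/6 cannot become 1/5 by dropping one.
- A DLT-free patient who misses doses in those cycles is judged by the fixed 75%/100% rule, and a delay after cycle 2 has no bearing on DLT evaluability.

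The final MTD estimate uses the same DLT-evaluable patients, so the sentence could reach it only by overriding SAP 4.1.

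**Conclusion.** SAP 6.1 is wrong as written: it contradicts itself and conflicts with SAP 4.1 to 4.3. The consequence is an undefined route for excluding patients, mainly from the efficacy and safety summaries by dose level. In the illustrations, one or two exclusions move ORR by about 3 to 6 points in most cases, and by 16.7 points when the only responder among six is removed. The responder counts and the numbers dropped are assumptions; the documents give no count of COVID-affected patients. The practical effect is modest in a descriptive Phase 1 study. The documents show neither that exclusions will be guided by outcome nor that dose-escalation decisions are at risk.

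**What to change.** Delete the case-by-case sentence from SAP 6.1. In its place:

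- state that patients with COVID-related delays or missed cycles remain in the Safety and Efficacy Populations as defined in SAP 4.2 and 4.3;
- state that SAP 4.1 alone decides DLT evaluability;
- add a listing of the affected patients.

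If the sponsor wants to keep some exclusion, the SAP should give objective criteria that do not depend on outcome for each population, name who applies them without sight of the results, document each decision, and show the results with all patients alongside.

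The cost is one deleted sentence, two short statements and one listing. No new data should be needed, because Protocol Appendix 7 already advises sites to record in the case report form when missing information is due to such circumstances. The sponsor gives up only a discretion that the population definitions do not provide for.
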